4.4.1 Entinostat (MS-275, SNDX-275)

4.3.1 Nivolumab (OPDIVO ®, BMS-936558; MDX-1106)

4.5 Supportive Care Guidelines and General Concomitant Medication

4.5.1 Supportive Care Guidelines

In general, concomitant medications and therapies deemed necessary for the supportive care and safety of the subject are allowed, provided their use is documented in the medical records and meets the dose modification guidelines outlined in **Section 5**.

The administration of any other therapies intended to treat the primary condition including chemotherapy and biologic agents is NOT permitted. Similarly, the use of other concurrent investigational drugs is not allowed.

Patients should receive appropriate supportive care measures as deemed necessary by the Investigator.

Blocking PD-1 function may permit the emergence of auto-reactive T cells and resultant clinical autoimmunity. Rash/pruritus, diarrhea/colitis, pneumonitis, hepatitis, and hypothyroidism were drug-related, presumptive autoimmune events noted in previous nivolumab studies.

All adverse events (AE) previously described in the Investigator's Brochures (IB) will be considered nivolumab-related AEs. For the purposes of this study, AE of unknown etiology, associated with drug exposure and consistent with an immune phenomenon, will be also considered nivolumab-related AE. Efforts should be made to rule out neoplastic, infectious, metabolic, toxin or other etiologic causes. Serological, immunological, and histological (biopsy) data should be used to support the diagnosis of an immune-mediated toxicity. Suspected nivolumab-related AEs must be documented on an AE or SAE CRF. Identification and treatment of nivolumab-related AEs can be found in **Appendix D**. Additional guidance can be found in the nivolumab IB.

Subjects who experience a grade 2 or higher nivolumab or entinostat-related AE should be discussed with the Principal Investigator (PI) and IND sponsor immediately

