4.8 Duration of Treatment and Criteria for Removal from Treatment

In general, treatment will continue until one of the following criteria are met:

- Disease progression. **NOTE**: Treatment may continue under the guidelines discussed in **Section 4.9**, as per opinion of the Investigators.
- The patient or legal representative (such as a parent or legal guardian) withdraws consent for treatment but not follow up.
- Intercurrent illness that prevents further administration of treatment.
- Unacceptable adverse events. If the study treatment has provided clinical benefit, the IND sponsor may approve trial continuation for patients experiencing entinostat-related toxicities that are not life threatening or of major clinical concern (such as pruritis or rash).
 NOTE: Assessment for discontinuation of entinostat may be made independently of nivolumab, continuation of entinostat may be considered with approval by the IND sponsor. There are instances where treatment with nivolumab may continue if entinostat has been discontinued. (Section 5.1)
- If in the opinion of the Investigator, a change or temporal or permanent discontinuation of therapy would be in the best interest of the patient. The Sponsor should be included in this decision.
- Noncompliance with trial treatment or procedure requirements.
- Patient becomes pregnant. All women of child bearing potential should be instructed to contact the investigator immediately if they suspect they might be pregnant (e.g., missed or late menstrual period) at any time during study participation. The investigator must immediately notify CTEP in the event of a confirmed pregnancy in a subject participating in the study.
- Treatment required with other chemotherapeutic or investigational anti-neoplastic drugs.

- Patient is lost to follow-up.
- In the case that a participant develops intolerance or side effect that is attributable to entinostat, the participant may, at his or her discretion, continue to receive only Nivolumab as otherwise indicated as long as they have received at least 1 full dose of both entinostat and nivolumab and nivolumab re-treatment criteria are met as outlined above.
- If nivolumab has to be permanently discontinued because drug-related toxicity, the patient will be permanently discontinued from entinostat treatment too.

The subject must be discontinued from the trial for any of the following reasons:

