5. DOSING DELAYS/DOSE MODIFICATIONS

In order to maintain dose-intensity and cumulative dose-delivery on this study, reasonable efforts will be made to minimize dose reduction and treatment delays as specified below.

Although entinostat and immune checkpoint blockade have distinct toxicity profiles, they do share some adverse events such as fatigue, nausea and diarrhea. There is the theoretical possibility that one agent may potentiate the other and hence drug causality will not always be clear. In the event of uncertainty, dose reductions and/or delays will follow the most conservative approach.

For any event which is apparent at baseline, the dose modifications will apply according to the corresponding shift in toxicity grade, if the investigator feels it is appropriate (e.g., if a subject has grade 1 asthenia at baseline which increases to grade 2 during treatment, this will be considered as a shift of 1 grade and treated as a grade 1 toxicity for dose modification purposes).

All toxicity grades below are described using the NCI Common Terminology Criteria for Adverse Events (CTCAE) version 4.03.

All discontinuations, relationships to treatment, and treatment decisions must be clearly documented in the medical record. Any questions should be discussed with the IND Sponsor.

Dose reductions due to toxicity are permanent. Dose escalation is not allowed. Dose reduction is not allowed for Nivolumab treatment.

NOTE: Tumor assessments should continue as per protocol even if dosing is delayed.

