6.1.2 Nivolumab

Blocking PD-1 function may permit the emergence of auto-reactive T cells and resultant clinical autoimmunity. Rash/pruritus, diarrhea/colitis, pneumonitis, hepatitis, and hypothyroidism were drug-related, presumptive autoimmune events noted in previous nivolumab studies.

For the purposes of this study, a nivolumab-related AE is defined as an AE of unknown etiology, associated with drug exposure and is consistent with an immune phenomenon. Efforts should be made to rule out neoplastic, infectious, metabolic, toxin or other etiologic causes. Serological, immunological, and histological (biopsy) data should be used to support the diagnosis of an immune-mediated toxicity. Suspected nivolumab-related AEs must be documented on an AE CRF. Identification and treatment of nivolumab-related AEs can be found in **Section 4.4** as well as in **Appendix D**. Additional guidance can be found in the nivolumab IB.

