6.3 Reporting Procedures for All Adverse Events

The Investigator is responsible for ensuring that all AEs observed by the Investigator or reported by patients are properly captured in the patients' medical records and reported on the eCRF. The evaluation time period for all adverse events is from the first dose of the investigational agent to at least 30 days after the last dose of entinostat or nivolumab, or until resolution of all acute toxicities associated with study drug administration, whichever is longer, with the exception of SAEs, which must be documented through 100 days following cessation of treatment, or 30 days after the initiation of a new anticancer therapy, whichever is earlier.

The following AE attributes must be assigned by the Investigator:

• event description (with detail appropriate to the event);

- seriousness;
- dates of onset and resolution;
- severity;
- assessment of relatedness to entinostat and to nivolumab; \Box the action taken.

Laboratory abnormalities: Laboratory abnormalities present at the screening visit will be recorded as pre-treatment signs and symptoms. After study treatment administration, all grade 3 and 4 clinical laboratory results that represent an increase in severity from baseline will be reported as AEs. A grade 1 or 2 clinical laboratory abnormality should be reported as an AE only if it is considered clinically significant by the investigator (induce clinical signs or symptoms or require therapy)

The Investigator may be asked to provide follow-up information, discharge summaries, and extracts from medical records.

If applicable, the study drug relationship will be assessed by means of the question: "Is there a reasonable possibility that the event may have been caused by one of the two drugs based on mechanism of action and/or toxicity profile, or by the combination of entinostat with nivolumab?" The relationship of an AE to the administration of the study drug is to be assessed by the investigator according to the following definitions:

- No (unrelated, not related, no relation): The time course between the administration of study drug and the occurrence or worsening of the adverse event rules out a causal relationship and another cause (concomitant drugs, therapies, complications, etc.) is suspected.

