duration of response is defined as the number of weeks from the start date of PR or CR (whichever response is recorded first) and subsequently confirmed to the first date that recurrent or progressive disease or death is documented. In such cases, recurrent or progressive disease will be assessed relative to the smallest tumor measurements recorded since the start of study treatment. The primary analysis of duration of response will be based on the time point responses, best overall response, and PD status that are determined by the review of the investigator

DOR will be summarized descriptively using the Kaplan-Meier method with 95% confidence intervals (CIs)

• The safety analysis will be performed in all subjects who receive any amount of study drug. A baseline measurement and at least 1 laboratory or other safety-related measurement obtained after at least 1 dose of study treatment may be required for inclusion in the analysis of a specific safety parameter (e.g., lab shifts from baseline).

A complete list of all AE data will be provided along with an assessment of NCI CTCAE grade and relationship to study drug. The incidence of AEs will be tabulated by subgroups of interest (e.g. grade 3 or higher, organ class, relationship to study drug).

For analyses at the individual level, the highest grade and relationship to study drug will be assumed if multiple events have occurred.

Toxicity will be tabulated by type and grade and will be summarized with descriptive statistics. Other safety data will be assessed in terms of physical examination, clinical chemistry, hematology, vital signs, and ECGs. Negative binomial regression and Cox proportional hazards models will be used to assess the rate of AE and time to first toxicity, respectively.

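### Section 4.5.1 makes every adverse event listed in an Investigator's Brochure nivolumab-related, which contradicts 6.1.2 and 6.3, and 12.3.2 does not say which rule its relationship tables follow

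*Combined protocol and SAP*

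**What the plan says.** Four parts of the combined protocol and SAP bear on what counts as nivolumab-related.

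- **4.5.1 Supportive Care Guidelines:** "All adverse events (AE) previously described in the Investigator's Brochures (IB) will be considered nivolumab-related AEs". The next sentence widens the class: "AE of unknown etiology, associated with drug exposure and consistent with an immune phenomenon, will be also considered nivolumab-related AE". The paragraph then adds: "Efforts should be made to rule out neoplastic, infectious, metabolic, toxin or other etiologic causes".
- **6.1.2 Nivolumab:** a near-repeat of that paragraph without the brochure sentence. Here "a nivolumab-related AE is defined as an AE of unknown etiology, associated with drug exposure and is consistent with an immune phenomenon".
- **6.3 Reporting Procedures for All Adverse Events:** the attributes the investigator must assign include "assessment of relatedness to entinostat and to nivolumab". The yes/no definitions turn on time course and on whether another cause is suspected or identifiable. One listed factor is that the event should come after the drug.
- **12.3.2 Analysis of Secondary Endpoints:** "The incidence of AEs will be tabulated by subgroups of interest (e.g. grade 3 or higher, organ class, relationship to study drug" and similar groupings. For patient-level analyses with several events, the highest grade and relationship are assumed.

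Section 6.2.3 uses listing in the brochure for a different purpose: to decide whether an event is expected.

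**The concern.** Being listed in a brochure says that an event has been described before. It does not say that nivolumab caused this occurrence in this patient. The first sentence of 4.5.1 nevertheless turns listing into attribution. The exposure and immune conditions belong to the second sentence, which adds further events and does not restrict the first.

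Safety is the first secondary objective, and each cohort is a single arm. With no control group, attribution is the plan's main means of separating drug effects from background events. If staff apply different rules, or 4.5.1 is applied as written, the relationship tables will mix nivolumab toxicity with disease symptoms and entinostat effects. Section 5 itself says of the two treatments that "they do share some adverse events such as fatigue, nausea and diarrhea". The patient-level convention in 12.3.2 adds to this: one event labelled by rule is enough to make the patient a related case.

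Relatedness also enters the treatment rules. Unacceptable toxicity (4.3) and nivolumab delay and discontinuation (5.1, 5.1.4) refer to treatment-related or drug-related events. Under 4.8, "If nivolumab has to be permanently discontinued because drug-related toxicity, the patient will be permanently discontinued from entinostat treatment too", whereas intolerance attributed to entinostat may leave nivolumab running. An inconsistent label could therefore affect which rule a patient falls under.

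**Working it through.** The plan states no figure that depends on the attribution rule, so there is none to reproduce. The check is a comparison of wording, followed by an illustration.

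**1. The rules side by side**

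| Input to the decision | 4.5.1, first sentence | 6.1.2 | 6.3 |
|---|---|---|---|
| Listed in a brochure | sufficient | not used | not used |
| Exposure or timing | not used | required | required |
| Other possible cause | not used | must be unknown | weighed |
| Immune character | not used | required | not required |
| Judged per drug | no | nivolumab only | yes, each drug |

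The instruction in 4.5.1 to look for other causes does not say that finding one reverses the first sentence.

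**2. A test case**

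Take nausea in the lead-in, assuming nausea is listed. Section 4.2 gives fourteen days of entinostat alone. Section 6.3 collects adverse events from the first dose of investigational agent, and the study calendar has a toxicity assessment at lead-in Day -7. The event is therefore recorded before any nivolumab is given.

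- 4.5.1, first sentence: nivolumab-related.
- 6.1.2: not nivolumab-related, because there has been no nivolumab exposure.
- 6.3: not nivolumab-related, because the event precedes the drug.

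**3. What the 4.5.1 rule measures**

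Let b be the proportion of patients with a listed event from causes other than nivolumab, and a the proportion with it caused by nivolumab, taken as independent. Every occurrence gets the label, so

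labelled rate = 1 − (1 − b)(1 − a),

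which is the all-cause rate. The share of labelled patients with a nivolumab-caused event is a divided by that rate.

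**4. Illustration with 27 patients per cohort (12.1)**

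Section 6.1.1 gives nausea in a lung-cancer trial as 49% on erlotinib plus entinostat and 25% on erlotinib plus placebo. The 10% value and all values of a are assumptions.

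- b = 10%, a = 0: 27 × 0.10 = 2.7 patients labelled.
- b = 25%, a = 0: 27 × 0.25 = 6.75, about 7 patients.
- b = 49%, a = 0: 27 × 0.49 = 13.2, about 13 patients.
- b = 25%, a = 10%: 1 − 0.75 × 0.90 = 32.5% labelled; nivolumab-caused share 0.10 / 0.325 = 31%.
- Lowest share over b = 10–49% and a = 5–20%: at b = 49%, a = 5%, the rate is 1 − 0.51 × 0.95 = 51.6% and the share 0.05 / 0.516 = 10%.
- Highest share over the same range: at b = 10%, a = 20%, the rate is 1 − 0.90 × 0.80 = 28% and the share 0.20 / 0.28 = 71%.

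In the three lines with a = 0, nivolumab caused none of the labelled events.

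**The case against.** A reader might infer that this trial cannot measure nivolumab toxicity at all. The documents do not support that, for these reasons.

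- Nothing makes 4.5.1 the governing rule. It is a supportive-care paragraph that leads to the management algorithms. Recorded attribution is set out in 6.3, drug by drug, and the serious adverse event form in Appendix F has separate columns for entinostat, nivolumab and underlying disease.
- 4.5.1 itself asks for other causes to be ruled out and for laboratory and biopsy support.
- 12.3.2 names no nivolumab-specific rate. It also provides a full event list with grade and relationship, and tables by type and grade. The primary endpoint is response, and 6.12 has no formal safety stopping rule.
- The brochures' contents are not in the documents, and it is unclear whether the plural covers entinostat's brochure. The 25% comes from lung-cancer patients on erlotinib plus placebo, so it is not a background rate for this population.
- Many treatment rules are keyed to treatment-related events, so moving an event from one drug to the other would often leave the trigger unchanged. Section 5 also says uncertain causality is handled conservatively.

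These points limit the consequence and make the sizes illustrative. They do not remove the contradiction. 4.5.1 also directs which events go on the case report forms, so it is not purely management advice. No section says that 6.3 overrides it, and 12.3.2 does not choose between them.

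**Conclusion.** The contradiction is real. Sections 4.5.1, 6.1.2 and 6.3 give different answers for the same event, and the analysis section does not say which it uses. This is more than missing detail, because one of the stated rules gives a wrong attribution when followed.

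The consequence is conditional. If 4.5.1 is applied, the nivolumab-related rate for any listed event is its all-cause rate, lead-in events are included, and the highest-relationship convention carries the error into patient-level summaries. If 6.3 is applied, none of this follows. No stated figure in the plan changes. The illustrative range of about 3 to 13 of 27 patients for nausea assumes that nausea is listed and takes event rates from 10% to 49%, none of them known for this population.

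**What to change.** - Delete the brochure sentence in 4.5.1, or restrict it to expectedness as in 6.2.3.
- State in 12.3.2 that the relationship tables use only the investigator's per-drug assessment under 6.3, tabulated separately for entinostat and nivolumab.
- State that an event starting before the first nivolumab dose and not worsening after it is not tabulated as nivolumab-related.
- Report all-cause events beside the related ones.
- Reconcile the wording of 4.5.1, 6.1.2 and 6.3, and the drug-related and treatment-related terms in 4.3, 4.8, 5.1 and 5.1.4. No view is taken here on the clinical rules themselves. Adopting 6.1.2 as the common definition would conflict with using 6.3 and could leave out non-immune nivolumab toxicity.

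While editing 6.3, close a gap in its two categories: an event with a compatible time course and another possible cause fits neither yes nor no.

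The cost is an amendment to wording. Per-drug relatedness and onset dates are already required by 6.3, so no new data are needed. Events already attributed under 4.5.1 would have to be re-checked.

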4.5.2 Hypersensitivity/Infusion Reactions

4.5.2.1 Entinostat

Hypersensitivity reactions should be managed as per standard of care at the treating institution. Severe reactions, such as hypotension requiring treatment, dyspnea requiring bronchodilators, angioedema or generalized urticaria require immediate discontinuation of study drug administration and aggressive symptomatic therapy.

Subjects who experience a severe hypersensitivity reaction to treatment should not be rechallenged.

4.5.2.2 Nivolumab

Nivolumab is a fully human monoclonal immunoglobulin (Ig) G4 antibodies. Subjects should be closely monitored for potential AEs during antibody infusion and potential AEs throughout the study.

Since nivolumab contains only human immunoglobulin protein sequences, it is unlikely to be immunogenic and induce an infusion or hypersensitivity reaction. However, if such a reaction were to occur, it might manifest with fever, chills, rigors, headache, rash, pruritus, arthralgia, hypo- or hypertension, bronchospasm, or other symptoms. All grade 3 or 4 infusion reactions should be reported within 24 hours to the IND Sponsor and BMS and Syndax as an SAE if the criteria are met. Infusion reactions should be graded according to CTCAE (version 4.03) guidelines. Treatment recommendations are provided below and may be modified based on local treatment standards and guidelines as appropriate:

For Grade 1 symptoms: (Mild reaction; infusion interruption not indicated; intervention not indicated).
 Remain at bedside and monitor subject until recovery from symptoms. The following

Remain at bedside and monitor subject until recovery from symptoms. The following prophylactic premedications are recommended for future infusions: diphenhydramine 50 mg (or equivalent) and/or paracetamol 325 to 1000 mg (acetaminophen) at least 30 minutes before additional nivolumab administrations.

• For Grade 2 symptoms: (Moderate reaction requires therapy or infusion interruption but responds promptly to symptomatic treatment [e.g, antihistamines, non-steroidal antiinflammatory drugs, narcotics, corticosteroids, bronchodilators, IV fluids]; prophylactic medications indicated for 24 hours).

Stop the nivolumab infusion, begin an IV infusion of normal saline, and treat the subject with diphenhydramine 50 mg IV (or equivalent) and/or paracetamol 325 to 1000 mg (acetaminophen); remain at bedside and monitor subject until resolution of symptoms. Corticosteroid or bronchodilator therapy may also be administered as appropriate. If the infusion is interrupted, then restart the infusion at 50% of the original infusion rate when symptoms resolve; if no further complications ensue after 30 minutes, the rate may be increased to 100% of the original infusion rate. Monitor subject closely. If symptoms recur then no further nivolumab will be administered at that visit. Administer diphenhydramine 50 mg IV, and remain at bedside and monitor the subject until resolution of symptoms. The amount of study drug infused must be recorded on the electronic case report form (eCRF). The following prophylactic premedications are recommended for future infusions: diphenhydramine 50 mg (or equivalent) and/or paracetamol 325 to 1000 mg (acetaminophen) should be administered at least 30 minutes before additional nivolumab administrations. If necessary, corticosteroids (recommended dose: up to 25 mg of IV hydrocortisone or equivalent) may be used.

For Grade 3 or Grade 4 symptoms: (Severe reaction, Grade 3: prolonged [e.g., not rapidly responsive to symptomatic medication and/or brief interruption of infusion]; recurrence of symptoms following initial improvement; hospitalization indicated for other clinical sequelae [eg, renal impairment, pulmonary infiltrates]). Grade 4: (life threatening; pressor or ventilatory support indicated).

Immediately discontinue infusion of nivolumab. Begin an IV infusion of normal saline, and treat the subject as follows. Recommend bronchodilators, epinephrine 0.2 to 1 mg of a 1:1,000 solution for subcutaneous administration or 0.1 to 0.25 mg of a 1:10,000 solution injected slowly for IV administration, and/or diphenhydramine 50 mg IV with methylprednisolone 100 mg IV (or equivalent), as needed. Subject should be monitored until the investigator is comfortable that the symptoms will not recur.

Nivolumab will be permanently discontinued. Investigators should follow their institutional guidelines for the treatment of anaphylaxis. Remain at bedside and monitor subject until recovery from symptoms. In the case of late-occurring hypersensitivity symptoms (eg, appearance of a localized or generalized pruritus within 1 week after treatment), symptomatic treatment may be given (eg, oral antihistamine, or corticosteroids).

In the case of late-occurring hypersensitivity symptoms (e.g., appearance of a localized or generalized pruritus within 1 week after treatment), symptomatic treatment may be given (e.g., oral antihistamine, or corticosteroids). Additional treatment prior to next dose as per guidelines above.

Please note that late occurring events including isolated fever and fatigue may represent the presentation of systemic inflammation. Please evaluate accordingly.

Nivolumab-related infusion reactions and adverse events must resolve prior to administration of entinostat.

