5.1.4 Nivolumab Treatment Discontinuation

Nivolumab treatment should be discontinued if any of the following criteria are met:

- Any Grade 2 treatment-related uveitis, eye pain, or blurred vision that does not respond to topical therapy and does not improve to Grade 1 severity within 2 weeks of starting therapy requires systemic treatment
- Any Grade 3 non-skin, drug-related AE lasting > 7 days, with the following exceptions:
 - Grade 3 treatment-related uveitis, pneumonitis, bronchospasm, diarrhea, colitis, neurologic toxicity, hypersensitivity reaction, or infusion reaction of any duration requires discontinuation
 - Grade 3 treatment-related endocrinopathies (except for adrenal insufficiency) adequately controlled with only physiologic hormone replacement DO NOT require discontinuation
 - Grade 3 fatigue that lasts >14 days
- Grade 3 treatment-related thrombocytopenia > 7 days OR that is associated with bleeding requires discontinuation
- Any treatment-related liver function test (LFT) abnormality that meets the following criteria, require discontinuation:
 - Total bilirubin $> 5 \times ULN$
 - Concurrent AST or ALT \ge 3 × ULN and total bilirubin > 2 × ULN
- Any treatment-related liver function test (LFT) abnormality that meets the following criteria, require discontinuation:
 - AST or ALT >5 x ULN in patients with AST/ALT level within normal limits at baseline
 - AST or ALT >10 \times ULN in patients with AST/ALT level more than 1 and up to 3 times ULN at baseline
 - Total bilirubin >3 x ULN irrespective of baseline levels

- Concurrent AST or ALT \geq 3 \times ULN and total bilirubin > 2 \times ULN, irrespective of baseline levels
- Any Grade 4 treatment-related AE or laboratory abnormality, except for the following events which DO NOT require discontinuation:
 - Grade 4 amylase or lipase abnormalities that are not associated with symptoms or clinical manifestations, or radiographic signs of pancreatitis.
 - Isolated grade 4 electrolyte imbalances/abnormalities that are not associated with clinical sequelae and are corrected with supplementation/appropriate management within 72 hours of their onset.
 - Grade 4 lymphopenia and leukopenia.

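### Symptoms that recur when a nivolumab infusion is restarted fall under a visit-only stop and also under the printed Grade 3 criterion, which ends both study drugs

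*Combined protocol and SAP*

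**What the plan says.** Section 4.5.2.2 describes a Grade 2 infusion reaction as follows: "Moderate reaction requires therapy or infusion interruption but responds promptly to symptomatic treatment". The management text for that grade continues: "If the infusion is interrupted, then restart the infusion at 50% of the original infusion rate when symptoms resolve". If there is no further trouble the rate may go back up. If there is, the instruction is: "If symptoms recur then no further nivolumab will be administered at that visit". The paragraph closes by recommending premedication before later nivolumab doses.

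The next paragraph covers Grades 3 and 4. Its description of Grade 3 includes "recurrence of symptoms following initial improvement; hospitalization indicated for other clinical sequelae". The consequence for these grades is: "Nivolumab will be permanently discontinued".

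Other sections attach further consequences to the grade:

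- Section 5.1.4, in its list of Grade 3 treatment-related events, ends with "hypersensitivity reaction, or infusion reaction of any duration requires discontinuation".
- Section 4.8, repeated in 5.1.4, states: "If nivolumab has to be permanently discontinued because drug-related toxicity, the patient will be permanently discontinued from entinostat treatment too".
- Section 4.5.2.2 states: "All grade 3 or 4 infusion reactions should be reported within 24 hours". That sentence goes on to make the report to the sponsor and the two companies an SAE report where the SAE criteria are satisfied.
- Section 12.3.2 tabulates adverse events by subgroups, one of which is Grade 3 and above.

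**The concern.** A nurse or physician handling a recurrence would find two instructions in adjacent paragraphs. One limits the stop to that visit and speaks of later infusions. The other uses words that fit the same event, and its grade carries a permanent stop of nivolumab and, through 4.8, of entinostat.

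Three things depend on which paragraph is followed. The first is whether the patient is exposed to nivolumab again or loses both drugs. The second is the grade recorded, and so the count of Grade 3 or higher events in the safety tables; safety is a secondary objective. The third is whether the event comes under the sentence on reporting Grade 3 or 4 infusion reactions within 24 hours.

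**Working it through.** The plan has no figure to reproduce here. The check is to follow one patient through the text.

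1. **Start.** The patient has a moderate reaction, the infusion is interrupted, and symptoms respond promptly. This fits the Grade 2 description in 4.5.2.2.
2. **Restart.** The infusion may be resumed only after symptoms have resolved. Any return of symptoms on restart is therefore, by construction, a return after improvement.
3. **Recurrence under the Grade 2 paragraph.** Nivolumab stops for that visit. Nothing there mentions permanent discontinuation, and the advice on premedication looks ahead to later doses.
4. **Recurrence under the Grade 3 description.** The features are separated by semicolons. Read as alternatives, recurrence after improvement is enough by itself, and step 2 shows that it is met.
5. **Consequences of Grade 3.** Section 4.5.2.2 ends nivolumab permanently. Section 5.1.4 does so separately, whatever the duration. Because the cause is drug-related toxicity, 4.8 and 5.1.4 then end entinostat.

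| | Grade 2 paragraph | Grade 3 description |
|---|---|---|
| Nivolumab | stopped for the visit | stopped permanently |
| Entinostat | not affected | stopped permanently (4.8, 5.1.4) |
| Safety table (12.3.2) | Grade 2 if not regraded | Grade 3 or higher |
| Grade 3 or 4 reporting sentence (4.5.2.2) | outside | inside, tied to SAE criteria |

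6. **Search for an exemption.** No visible sentence keeps recurrence on restart at Grade 2 or exempts it from 5.1.4. Section 4.5.2.2 lets the treatment recommendations be adapted to local standards. That clause does not assign a grade and does not relax 5.1.4 or 4.8.

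**Size.** The documents give no incidence of infusion reactions or of recurrence on restart. Purely as an assumption, take reactions in 3% to 10% of patients and recurrence in a quarter of those. Enrolment is 2 × 27 = 54 to 2 × 33 = 66.

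- Low: 54 × 0.03 × 0.25 = 0.4 patients in the whole trial.
- High: 66 × 0.10 × 0.25 = 1.65, or about 1.7 patients.

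One reclassified patient changes a cohort's Grade 3 or higher proportion by 1/27 = 3.7 percentage points, or 1/33 = 3.0 points at full enrolment, if that patient has no other Grade 3 event.

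**The case against.** The strongest reply is that the paragraphs can be read in sequence. The Grade 2 paragraph does not grade the recurrence; it only says what to do at the bedside. Its premedication advice covers every Grade 2 patient, including those who restart without trouble. Section 4.5.2.2 names CTCAE 4.03 as the grading standard. On this reading the infusion stops, the event is then graded 3, and the permanent stop follows. This is possible, and it is right that the Grade 2 paragraph nowhere says the event stays Grade 2. But the visit-limited instruction is then incomplete for an event that meets the printed Grade 3 wording, and no cross-reference tells the reader to move on.

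Second, there are safeguards. Section 4.5.1 calls for immediate discussion with the principal investigator and IND sponsor for any related event of Grade 2 or higher. The trial has one institution (4.2) and weekly safety meetings (11.4). These make inconsistent handling less likely. They do not state the grade or the consequence.

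Third, the reporting effect is limited. The 24-hour sentence in 4.5.2.2 is tied to the SAE criteria, and 6.4 requires all SAEs to be reported within 24 hours whatever their grade. This stands: a change of grade need not change what is reported.

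Fourth, the content of 5.1.3 and the algorithms in Appendix D cannot be seen in the public text. A clarification there cannot be ruled out, which is a reason for moderate confidence.

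**Conclusion.** The two paragraphs need reconciling. As printed, recurrence after restart can be handled as a stop for one visit or as permanent loss of both drugs, and recorded as Grade 2 or as Grade 3 or higher. The conclusion assumes that the listed Grade 3 features are alternatives and that the unseen 5.1.3 and Appendix D do not settle the matter. Severity is minor and confidence moderate. Few patients are likely to be affected; the range of 0.4 to 1.7 rests wholly on assumed rates.

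A reader might infer that the conflict also weakens the primary response analysis or its power. The documents do not support that. Under 12.3.1 the evaluable population is everyone with at least one dose of entinostat, so a patient who stops early stays in it. Section 12.2 allows replacement of a patient who leaves for toxicity before completing the first cycle without progression. With no incidence given, and no basis for assuming that affected patients would not respond, no loss of power can be derived.

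**What to change.** Reconcile the Grade 2 paragraph, the Grade 3 description and the permanent-stop sentence in 4.5.2.2 with 5.1.4 and 4.8, so that recurrence of symptoms after a same-day restart has one grade and one consequence. Cross-refer 4.5.2.2 and 5.1.4, and check that 5.1.3 and Appendix D agree. Use the agreed grade on the case report form, in the safety tables and for reporting. Which grade and which consequence apply is for the sponsor's clinicians to decide.

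The cost is about one sentence in 4.5.2.2 and a cross-reference in 5.1.4 at the next amendment, with no extra patients or procedures.
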